We hypothesize that preterm infants supplemented with early physiologic doses of L-carnitine while on parenteral nutrition will have improved short-term growth parameters and significantly higher neurobehavioral scores when compared with control infants.

Primary Aims:

To determine whether carnitine supplementation is associated with:

- 1. Decreased percent weight loss within the first two weeks of life and decreased length of time to regain birthweight.
- 2. Improved performance on the NICU Network Neurobehavioral Scale (NNNS) at 40 weeks postmenstrual age (+/- 2 weeks).

Secondary Aims:

To determine whether carnitine supplementation is associated with:

- 1. Increased rate of growth of head circumference within the first month of life and increased food efficiency (weight gain/calorie intake) during the supplementation period.
- 2. Normalization of the serum carnitine profile at two weeks of life, compared with infants born at a post-menstrual age 2 weeks later.
- 3. Enhanced brain maturation as measured by amplitude-integrated EEG (aEEG) measurements obtained during the hospital course
- 4. Fewer abnormal findings, better brain growth, white matter development and brain metabolism on brain magnetic resonance imaging (MRI) at 36-40 weeks' corrected age (prior to hospital discharge)

Because of the potential for systemic effects of L-carnitine supplementation, we will also monitor those variables which showed significant difference in our prior study: rates of proven infection, hearing screen failure and PDA ligation.

Primary Outcomes:

- 1. Length of time to regain birthweight,
- 2. Percent weight loss in the first two weeks of life,
- 3. Neurodevelopmental scores on the NICU Network Neurobehavioral Scale (NNNS) at 40 weeks post-menstrual age (+/- 2 weeks)

Methods/Design:

This is a prospective, randomized controlled clinical trial involving infants with gestational age (GA) <32 wks who are born at either the Jack D. Weiler Hospital or the Wakefield Division of Montefiore and admitted to theirNeonatal Intensive Care Unit. Informed consent will be obtained from the parents of eligible patients as early as possible within 72 hours of birth. Infants whose parents have signed an informed consent form will be randomized to receive either carnitine supplementation (50 µmol/kg/day) versus placebo within 72-96 hours of birth.

Inclusion criteria:

- Infants born <32weeks' gestation
- Exclusion criteria:
 - Presence of

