 - o potentially life-threatening congenital anomaly
 - o known hereditary metabolic disorder
 - o known chromosomal abnormality
 - teratogen exposure with symptomatic substance withdrawal
 - o congenital viral infections
 - microcephaly
 - Grade IV intraventricular hemorrhage (IVH) or seizures documented within first 72 hours of birth
 - Critically-ill with life expectancy less than 72 hours
 - Unable to obtain consent within 72 hours of birth
 - Enrolled in another intervention trial

Participant recruitment: Parents or guardians of infants who meet study criteria will be approached regarding the study as early as possible within 72 hours of the infant's birth. Informed consent will be obtained by study investigators and coordinators. Permission will be requested to re-contact the families after completion of the supplementation study for follow-up.

Randomization: As previously described by Pande et al., enrolled patients will be randomized to either the treatment group (L-carnitine, 50 µmol/kg/day) or placebo group (5% glucose, similar volume as the L-carnitine group).²⁸ Patients who meet study entry criteria and have signed informed parental/guardian consent will be enrolled in the study. Because gestational age and small for gestational age (SGA) status will impact our outcome measures, we will ensure they are equally distributed in the arms of the study by stratifying based upon these variables. We will analyze the two study arms using an intent-to-treat analysis. Therefore, enrolled patients will be stratified into fourgroups: gestational age 23 to 26 6/7 weeks, gestational age 27 to 29 6/7weeks, gestational age 30 to 31 6/7 weeks and small for gestational age (SGA). Patients within each stratum will be randomized by the pharmacist using a computerized block-generation with sets of 4. In the case of multiple births, all infants must meet study criteria, and the infants will be randomized as a set. One infant of the multiple-birth set will be randomly chosen for inclusion in the analysis. A recruitment log of all screened infants will be maintained. Clinicians and the nursing staff will be unaware of the arm of the treatment protocol to which the patient is assigned. Codes will be unblinded only after all patients have reached the study end-point, or at the request of the Data Safety Monitoring Board.

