We will assess neurodevelopmental outcomes at 18-24 months corrected age using the Bayley Scales of Infant and Toddler Development, Third Edition (BSID-III). The BSID-III is a validated instrument used for assessing the development of Cognitive, Language (Receptive and Expressive), Motor (Fine and Gross), Social-Emotional and Adaptive skills in infants and toddlers. This normative assessment yields scaled scores, composite scores, percentile ranks, and developmental age equivalents, all of which provide important information about a child's level of functioning relative to his or her same-age peers. While Cognitive, Language and Motor skills are assessed through direct interaction with the child, Social-Emotional and Adaptive skills are obtained from parent report. Because the BSID-III is commonly used for identifying children who are in need of early intervention due to developmental delays, this instrument will be sensitive to detecting the types of developmental issues we often see in very young children born preterm. Additionally, at the follow-up visit at 18-24 months corrected age, we will administer two parental questionnaires: the Modified Checklist for Autism in Toddlers (M-CHAT) and the Child Behavior Checklist (CBCL). M-CHAT is a parent-report checklist developed to screen children for early signs of autistic features. The CBCL is a standardized, well-validated parent-report questionnaire developed to assess various maladaptive behavioral and emotional problems in young children.

Record confidentiality: Records relating to the study will be kept in a secure location, to which only study personnel will have access. Records will be kept in a locked file cabinet in the neonatology offices and in a password-protected computer.

Statistical Analyses:

Statistical analysis will be performed with the assistance of a statistician.

Sample size:

We plan to recruit a total of 150 infants for our study over approximately 36months' time. This number is based upon an expected attrition of approximately 50 infants over the course of the study and a desired sample size of 100 infants. The inclusion of 100 infants in our study (50 in each study arm) will allow us to detect a moderate difference in our primary outcomes at a significance level of 0.05 with a power of 0.8. (0.5 SD; α = .05; power = .80).

Primary Outcomes	Mean	Standard Deviation	0.5 x Standard Deviation
Percent weight loss*	10.8%	6.2	3.1
Time to regain	11.3 days	4.3	2.2
birthweight*			

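### All SGA infants share one randomisation stratum, so gestational age is left to chance among them, and the stratum of a multiple-birth set with SGA and non-SGA siblings is undefined

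*Combined protocol and SAP*

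**What the plan says.** In the combined protocol and SAP, under Methods/Design, the Randomization paragraph gives the reason for stratifying: both variables affect the outcomes, and "we will ensure they are equally distributed in the arms of the study by stratifying based upon these variables". It then says that "enrolled patients will be stratified into fourgroups". The first two are the bands 23 to 26 6/7 and 27 to 29 6/7 weeks; the last two are "gestational age 30 to 31 6/7 weeks and small for gestational age (SGA"). Within each stratum, infants are "randomized by the pharmacist using a computerized block-generation with sets of 4".

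For multiple births, "all infants must meet study criteria, and the infants will be randomized as a set", and "One infant of the multiple-birth set will be randomly chosen for inclusion in the analysis". The paragraph does not say which stratum's list a set uses when siblings differ in SGA status, how many block places a set takes, or when the analysed infant is drawn relative to allocation.

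Under Outcome Measures, the continuous outcomes are compared by t-test or rank-sum test. The only adjusted models named are logistic; their covariates include gestational age and birth weight but not SGA status.

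**The concern.** A full cross of three gestational-age bands with SGA (yes/no) has 3 × 2 = 6 cells. The plan has four groups. For these to be mutually exclusive, SGA has to override the gestational-age band; the plan does not state this, but no other reading gives four groups. A 24-week and a 31-week SGA infant then draw from the same block list, and nothing balances gestational age between arms inside that list.

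The multiples rule leaves a second gap. Siblings normally share a gestational age, so a set can span two strata only by differing in SGA status. When it does, the pharmacist has no written rule for which list to use, and the infant later drawn for analysis may belong to the other stratum.

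At stake are chance balance and precision on a variable that the plan itself calls prognostic. The analysis as written does not clearly recover the loss, because its adjusted models do not fit the continuous primary outcomes.

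**Working it through.** The plan gives no figure for arm balance, so there is none to reproduce.

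**From the documents:** three bands plus SGA; blocks of 4; 1:1 allocation; 100 infants analysed and 150 recruited (Sample size).

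**Assumed, because the documents do not give them:** SGA share 10, 20 or 30%; 25/35/40% of infants in the three bands, independent of SGA; gestational age uniform within 23–27, 27–30 and 30–32 weeks.

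**Step 1: approximation by hand.** The band means are 25, 28.5 and 31, so the overall mean is 0.25×25 + 0.35×28.5 + 0.40×31 = 28.625 weeks.

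- Within-band variance: W = 0.25×16/12 + 0.35×9/12 + 0.40×4/12 = 0.73.
- Between-band variance: B = 0.25×3.625² + 0.35×0.125² + 0.40×2.375² = 5.55.
- Total: T = 6.28.

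If every block fills, the RMS arm difference in mean gestational age for N infants with SGA share s is:

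- no stratification: √(4T/N) = √(0.04×6.28) = 0.50 weeks;
- six crossed cells: √(4W/N) = √(0.04×0.73) = 0.17 weeks;
- the plan's four strata: √(4[(1−s)W + sT]/N) = 0.23, 0.27 and 0.31 weeks for s = 10, 20 and 30%;
- inside the plan's SGA stratum: √(4T/(sN)) = 1.58, 1.12 and 0.91 weeks, the same formula as with no stratification.

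**Step 2: simulation with incomplete blocks.** 2,000 trials per setting, 100 infants, no multiples. RMS arm differences for SGA shares of 10 / 20 / 30%:

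| Quantity | No strata | Four strata (plan) | Six crossed cells |
|---|---|---|---|
| Mean gestational age, SGA infants (weeks) | 1.74 / 1.13 / 0.93 | 1.67 / 1.15 / 0.91 | 1.18 / 0.59 / 0.41 |
| Mean gestational age, all infants (weeks) | 0.51 / 0.50 / 0.49 | 0.24 / 0.28 / 0.32 | 0.20 / 0.20 / 0.20 |
| Number of SGA infants | 3.15 / 4.45 / 5.37 | 0.89 / 0.93 / 0.88 | 1.56 / 1.60 / 1.55 |

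A repeat run agreed to within 0.04 weeks and gave 0.21 for the whole trial with crossed cells. With 150 infants the whole-trial figures are 0.20 / 0.23 / 0.26 weeks for four strata, 0.16 for six and about 0.41 for none.

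**Step 3: reading the table.** Among SGA infants the plan's scheme matches no stratification. Over the whole trial it delivers most of the attainable reduction: (0.51−0.24)/(0.51−0.20) = 87%, (0.50−0.28)/(0.50−0.20) = 73%, and (0.49−0.32)/(0.49−0.20) = 59%. Its excess over six cells is 0.04 to 0.12 weeks, or 0.3 to 0.8 days.

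**Step 4: multiples.** Assume that 25% of analysed infants come from multiples, that 20% of those sets are SGA-discordant, that each set takes one block place, and that its stratum comes from a random sibling. Under four strata the RMS difference in SGA count rises from about 0.9 to 1.58 / 1.73 / 1.78, against 3.10 / 4.46 / 5.28 without strata. The band counts change by only about 0.1.

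**The case against.** The strongest reply is that the scheme already does most of its job. SGA has its own blocked stratum and is balanced to about one infant; gestational age is blocked among the non-SGA majority; and the excess imbalance over crossed cells is under one day of gestational age. The larger figures, above one week, apply only inside the SGA group, and no SGA subgroup analysis is planned. All of this stands.

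A reader might infer that stratification fails for SGA status too, or that the comparison is biased. Neither follows: the SGA count is tightly balanced, and allocation is random in every stratum.

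A reader might also take the mortality gradient under Risks and Discomforts (about 75% at 23 weeks, 24% at 24–26, 5% at 27–29) as proof that the growth and neurobehavioural results would shift. Those are unit-wide mortality figures; mortality is not a primary outcome, and the plan gives no slope of any primary outcome on gestational age. The size of an effect on results is therefore not shown.

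Eligibility is "Infants born <32weeks' gestation", with no floor, while the lowest band starts at 23 weeks. This is a drafting mismatch, and nothing suggests that many infants fall below it.

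The reply does not remove two facts: the promise of equal distribution is not met for gestational age among SGA infants, and the rule for discordant sets is missing.

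**Conclusion.** The point holds in limited form. Gestational age is left to chance within the SGA stratum, and whole-trial balance is looser than it need be: 0.24 to 0.32 weeks RMS, against 0.20 to 0.21 with crossed cells and about 0.50 with none. This is a modest loss of chance balance and precision. The figures rest on assumed SGA shares, band proportions and independence of SGA from gestational age, and they ignore attrition after randomisation. The pooled stratum follows from the plan's wording whatever the shares.

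For discordant sets the gap is mainly a missing operational rule. Its size depends on how common such sets are, which the documents do not give; under the assumptions tried, balance stays far better than without stratification.

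**What to change.** For infants not yet randomised, stratify by the three gestational-age bands crossed with SGA (yes/no): six cells, blocks of 4. For multiples, draw the infant to be analysed at random before allocation, randomise the set in that infant's stratum, and state how many block places a set takes. The lowest band can be reworded to match the eligibility criterion at the same time.

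The cost is a new pharmacy list, more incomplete blocks and slightly looser balance of SGA count: about 1.6 against 0.9 infants RMS, or 1.6/50 = 3.2 against 0.9/50 = 1.8 percentage points with 50 per arm. With few SGA infants the gain is partial: at a 10% share, crossed cells still leave about 1.2 weeks RMS among them.

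If recruitment is advanced, keep the four strata and prespecify linear regression of the continuous primary outcomes on arm, gestational age and SGA status. This needs no new list, only a change to Outcome Measures. The rule for multiples should be written down in either case.

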Study supplementation: Infants randomized to the treatment group will receive 50 µmol/kg/day of Lcarnitine intravenously for 2 weeks, and infants randomized to placebo will received 5% glucose, similar volume to the L-carnitine group. At two weeks, sufficient carnitine is provided in enteral feeds of either breast milk or infant formula. If no intravenous access is available before the supplementation endpoint, the equivalent dose of enteral study supplement (L-carnitine or placebo) will be administered.⁴¹ Parenteral and enteral nutrition will be provided according to standard NICU protocol.

Of note, as many as 10% of the infants in the study will likely continue to rely primarily on parenteral nutrition beyond the proposed two-week supplementation period. Enteral feeds may be withheld from these infants due to underlying illnesses such as sepsis or gastrointestinal disorders like necrotizing enterocolitis. Due to the presence of underlying illness, these infants are at an even higher risk for developing developmental delays.⁴²Therefore, in study patients who are not receiving adequate enteral nutrition (100 cc/kg/day of enteral intake) after 2-weeks of study supplements, carnitine supplementation will be continued until these infant are receiving adequate enteral feeds; at this point, their physiologic carnitine requirements will be met by enteral nutrition alone.

Timeline of Assessments:

- a. Within 72 hours of birth
 - i. Patient enrollment and initiation of study protocol

- ii. Initial carnitine panel drawn
- iii. Initial aEEG reading obtained within 2-3 days of study initiation
- iv. Study Supplement begins within 72-96 hours of birth
- b. Two weeks after study initiation
 - i. Study Supplement concludes (in a small sub-set of patients, study supplementation will be continued until enteral feeds reach 100 cc/kg/day)
 - ii. Follow-up carnitine panel drawn (in addition, as blood transfusions may impact carnitine levels, serum carnitine profiles will be drawn prior to blood transfusion administered between the first and second weeks of life)
- c. aEEG readings will be obtained within 2-3 days of study initiation and at the following post-menstrual ages: 28 weeks (if infant <27 weeks at birth), 32 weeks', 36 weeks', and at 40 weeks' (if infant is still admitted to the NICU).
- d. 36-38 weeks' corrected age
 - i. Cranial MRI
- e. 40 weeks GA (+/- 2weeks)
 - i. Neurodevelopmental assessment

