 enrollment and at the end of the intervention (and again if a blood transfusion is administered within this period) 5. Amplitude-integrated EEG readings – within 2-3 of study enrollment and at 28, 32, 36 and 40 weeks' post-menstrual age (dashed lines) 6. Hearing screens – OAE and BAER during the NICU course 7. Brain MRI at 36-40 weeks' GA 8. NNNS at term-equivalent follow-up visit 	3.	(Growth parameters, fluid and nutrition intake and important hospital events), also includes interview with mother to record demographic		96 hours 2 weeks
 study enrollment and at 28, 32, 36 and 40 weeks' post-menstrual age (dashed lines) 6. Hearing screens – OAE and BAER 6. Hearing screens – OAE and BAER 7. Brain MRI at 36-40 weeks' GA 8. NNNS at term-equivalent follow-up visit 	4.	enrollment and at the end of the intervention		28 weeks
during the NICU course 30 week 7. Brain MRI at 36-40 weeks' GA NICU Discharge 8. NNNS at term-equivalent follow-up visit Term-equivalent	5.	study enrollment and at 28, 32, 36 and 40 weeks'		32 weeks
8. NNNS at term-equivalent follow-up visit	6.	• •		36 weeks
	7.	Brain MRI at 36-40 weeks' GA		NICU Discharge
	8.	NNNS at term-equivalent follow-up visit	· ·····	Term- equivalent (due date)
	9.	corrected ago		18-24 months CGA

Serum carnitine profiles: Blood samples (dried blood spots) will be collected at study enrollment and again at two weeks of lifefor measurement of acylcarnitine profiles as well as total and free carnitine levels. Collected samples will be batched and shipped to Baylor College of Medicine. As blood transfusions may impact carnitine levels, these studies will be drawn prior to a blood transfusion required between the first and second weeks of life.

Study specimens will be stored and used for future research purposes provided parents give consent for the storage and future use of the samples. Clinical information will be linked to the study specimens.

Data collection: After study enrollment, medical history and baseline data will be collected for each infant enrolled in the study. Prospective data will be recorded on a weekly basis throughout the NICU stay and after discharge at specific time points. Data will be recorded on standardized case report forms (CRFs) organized into the following categories:

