These aEEG recordings are non-invasive and do not create additional risk for the patient. These aEEG readings will be performed by study personnel and will be provided at no additional cost to the patient.

MRI Brain Imaging

Imaging of the brain at term-equivalent is the standard of care for the evaluation of preterm infants prior to being discharged home. In our Neonatal Intensive Care Units, we routinely obtain brain MRI at \geq 36 weeks' corrected age (prior to discharge home). The MRI examination is performed in sleeping infants after they have been fed; therefore, sedation is not required for the procedure. MRI will be performed per routine protocol at 36 weeks' corrected age, prior to discharge home. Brain growth will be assessed on anatomical images, through manual segmentation of the basal ganglia, cerebellum and whole brain. White matter development will be assessed on diffusion tensor imaging (DTI), using the tract-based spatial statistics method. The DTI measures fractional anisotropy and mean diffusivity, which have previously been shown to be abnormal in ex-preterm children; these will be compared in multiple white matter regions (cerebral peduncle, posterior limb of the internal capsule, corona radiata, corpus callosum, and optic radiations).^{37,46,47}

Brain metabolism will be assessed using proton MR spectroscopy, obtained from both white matter (centrum semiovale) and gray matter (basal ganglia) structures. The relative concentrations of the brain metabolites choline, creatine and n-acetylaspartate (NAA) will be compared between control and carnitine-supplemented children. Each metabolite reflects specific cellular and biochemical processes. NAA is a neuronal marker and decreases with any disease that adversely affects neuronal integrity. Choline is a constituent of cell membranes and an intermediate of phospholipid metabolism. Choline levels on MR spectroscopy increase with increased membrane turnover, and are taken as a measure of cell proliferation. Creatine plays a role in maintaining energy-dependent systems in brain cells by serving as a reserve for high energy phosphates. Because the creatine peak remains fairly stable even in face of disease, it may be used as a control value.⁴⁸ In children born preterm, the NAA/Choline ratio at term-equivalent age correlates with later cognitive development.⁴³

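### The brain MRI window is inconsistent (upper limit 38 or 40 weeks), and no analysis of the quantitative MRI measures accounts for age at scan

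*Combined protocol and SAP*

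**What the plan says.** **Timing.** Four places in the combined protocol and SAP set the time of the scan.

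- Secondary Aims, item 4: "brain magnetic resonance imaging (MRI) at 36-40 weeks' corrected age (prior to hospital discharge".
- Timeline of Assessments, item (d): "36-38 weeks' corrected age".
- Individual Infant Timeline, item 7: "Brain MRI at 36-40 weeks' GA". The label here is GA rather than corrected age.
- MRI Brain Imaging: the unit's routine is a scan at or after "36 weeks' corrected age (prior to discharge home". For the study, "MRI will be performed per routine protocol at 36 weeks' corrected age, prior to discharge home". The same section adds that the routine will not be altered for the study.

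**Analysis.** The MRI section describes segmented volumes as the measure of brain growth, diffusion tensor imaging (fractional anisotropy, FA, and mean diffusivity, MD) as the measure of white matter development, and spectroscopy as the measure of brain metabolism. DTI and spectroscopy values are to be compared, and no covariate is named for any of the three. The Outcome Measures section gives an unpaired t-test or rank-sum test for continuous data, and Fisher's exact or chi-square tests for nominal data. It names one MRI outcome, the presence or absence of pathology on the discharge scan. Its only adjusted analysis is a logistic model with gestational age, birth weight, race, gender and Apgar scores.

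**The concern.** A scan at 39 weeks satisfies Secondary Aim 4 but falls outside item (d) of the timeline. Two readers could therefore apply different rules on which scans count, and the choice could be made after the data are seen.

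Aim 4 uses the quantitative measures as indicators of brain growth and development, so they can be expected to change over the weeks in which scans are allowed. Two infants with the same underlying course, scanned at 36 and at 40 weeks, would then differ for a reason unrelated to carnitine. Left out of the model, that difference becomes residual variance. Nothing in the statistical section removes it. The listed gestational age is the age at birth, recorded under patient demographics by obstetric estimate or Ballard score, and a logistic model does not fit a continuous volume, anisotropy value or metabolite ratio.

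**Working it through.** **1. The windows side by side**

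| Place | Lower limit (weeks) | Upper limit (weeks) |
|---|---|---|
| Secondary Aim 4 | 36 | 40, before discharge |
| Timeline of Assessments (d) | 36 | 38 |
| Individual Infant Timeline, item 7 | 36 | 40 |
| MRI section, routine | 36 | discharge only |
| MRI section, study scan | 36 | none besides discharge |

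All agree on 36 weeks as the start. They differ on the end.

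**2. Is there a figure in the plan to reproduce?** Not for MRI. The documents give no sample size, SD, effect or rate of change for any MRI measure. What follows is an illustration.

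**3. Inputs**

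- From the Sample size section: 50 infants per arm and an effect of 0.5 SD. These were set for the primary outcomes and are borrowed here.
- From Outcome Measures: two-sided significance level 0.05.
- Assumed: scan age spread evenly over a window of w weeks, and a measure that changes by b SD per week with b = 0.2 to 0.5, where the SD is that between infants at a fixed scan age.

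**4. Formulas**

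- SD of scan age = w/√12. For w = 4 this is 1.155 weeks; for w = 2 it is 0.577 weeks.
- Unadjusted SD = √(1 + b²w²/12).
- Standardised effect d = 0.5 / unadjusted SD.
- Power from the noncentral t distribution with 98 degrees of freedom and noncentrality d√(50/2) = 5d.

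**5. Results**

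| Window | b (SD/week) | Unadjusted SD | d | Power |
|---|---|---|---|---|
| Scan age in the model | any | 1.000 | 0.500 | 0.697 |
| 36-40 weeks | 0.2 | √(1 + 0.04 × 1.333) = 1.026 | 0.487 | 0.674 |
| 36-40 weeks | 0.5 | √(1 + 0.25 × 1.333) = 1.155 | 0.433 | 0.573 |
| 36-38 weeks | 0.2 | √(1 + 0.04 × 0.333) = 1.007 | 0.497 | 0.691 |
| 36-38 weeks | 0.5 | √(1 + 0.25 × 0.333) = 1.041 | 0.480 | 0.662 |

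The first row ignores the one degree of freedom spent on the covariate. Its 0.697 is below the 0.80 that the plan states for 50 per arm and 0.5 SD, because the test is two-sided; a one-sided test gives 0.799. That is a separate matter, and only the drop from 0.697 counts here.

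**6. If mean scan age differed between arms.** The unadjusted difference would shift by b times the gap in weeks. A gap of half a week, for example, would shift it by 0.1 to 0.25 SD. No such gap is given or implied in the documents.

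**The case against.** **A reader might count four conflicting scan times.** The text does not support that. Secondary Aim 4 and the Individual Infant Timeline agree on 36-40 weeks. In the MRI section, the scan at 36 weeks is described as following the routine just stated, so it reads naturally as shorthand for 36 weeks or later. The firm conflict is the upper limit of 38 against 40 weeks, and that conflict stands.

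**A reader might infer a bias against carnitine:** faster growth, earlier discharge, hence a younger and less mature brain at the scan. The documents do not support this. The Background reports that the group's previous trial, at the same dose, found no significant difference in average daily weight gain up to 36 weeks or up to discharge; the reported benefit was less weight loss during supplementation. No section reports or predicts earlier discharge. Discharge is a deadline for the scan and is not described as its trigger. What remains is narrower: randomisation does not guarantee balance in an age fixed after treatment starts, so a shift is possible, of unknown size and direction.

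**A reader might say that the plan commits the MRI measures to an unadjusted t-test.** Strictly, its list of continuous outcomes contains no MRI measure, and its covariate list is open-ended. The general sentence on unpaired comparison may cover them, but it is more exact to say that their model is unspecified. The gap is the same either way.

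**The remedy has a weakness.** Scan age is measured after randomisation. If treatment did move it, conditioning on it could itself mislead, since readiness for discharge may also reflect illness. This is a fair point and shapes the fix.

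**The loss may be small.** Over 36-38 weeks it is at most about 3.5 percentage points of power in the range shown, and MRI is one of four secondary aims.

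**Conclusion.** The concern holds as an inconsistency in the scan window together with a missing analysis model. The passages conflict on the upper limit and must be reconciled, and nothing in the plan adjusts the quantitative MRI measures for age at scan.

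The main cost is precision. From a power of 0.70, the loss is about 2 to 12 percentage points over 36-40 weeks (to 0.67-0.57) and about 1 to 3.5 points over 36-38 weeks (to 0.69-0.66). These figures rest on an assumed slope of 0.2-0.5 SD per week, an even spread of scan ages, and 50 scanned infants per arm taken from the primary-outcome calculation. A flatter slope, or scans clustered near 36 weeks, would make the loss smaller.

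A systematic bias in either direction is hypothetical. No primary outcome and no stated figure depends on this point. It should be corrected, but it does not threaten the trial's main conclusions.

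**What to change.** 1. Reconcile Secondary Aim 4, Timeline of Assessments (d), the Individual Infant Timeline and the MRI section to one window with explicit lower and upper limits, using one term for age. State how scans outside it are handled.
2. Record the scan date on the case report form, so that postmenstrual age at scan can be derived.
3. Prespecify, for each quantitative MRI measure (volumes, FA, MD, metabolite ratios), a linear model with treatment arm and postmenstrual age at scan.
4. Report the distribution of scan age by arm, and show the unadjusted comparison beside the adjusted one. If scan age differs between arms, interpret the adjusted result with caution, because the covariate arises after randomisation.

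The cost is wording, one recorded date and one covariate per model. No extra scans are needed.
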